1. OBJECTIVES OF THE INTERIM ANALYSIS F1

- 1. To measure and compare peanut intake and reactions to peanut (accidental or intentional ingestion) from end-of-treatment (T1 of PPOIT-003 study) to 24 months (F1) post-treatment:
 - in PPOIT vs OIT vs placebo and
 - in subjects with SU vs DWSU vs allergic.
- 2. To compare change from baseline in quality of life (PPOIT-003 study entry) at 24 months (F1) posttreatment:
 - in PPOIT vs OIT vs placebo groups and
 - in subjects with SU vs DWSU vs allergic.

2. BACKGROUND/INTRODUCTION

2.1. GENERAL STUDY INFORMATION

(refer to protocol version 4 dated 05 Oct 2021)

Study design

This is a multicentre follow-on study. There is no treatment intervention in this study. However, there will be study assessments performed including skin prick test (SPT) and blood tests. Subjects will remain blinded to their PPOIT-003 treatment allocation and will continue with peanut avoidance / ingestion according to the instructions they received at the end of treatment in PPOIT-003 as outlined below:

- Subjects who were classified as SU at T2 in PPOIT-003 (Group 1) were instructed to introduce • peanut into their diet ad libitum without specific instructions on how often or how much peanut to ingest.
- Subjects who were classified as desensitisation without SU at T2 in PPOIT-003 (Group 2) were instructed to ingest 1-2 peanuts each day to maintain desensitisation.
- Subjects who were classified as allergic at T1 in PPOIT-003 (Group 3) were instructed to continue with strict peanut avoidance.

The classification of these clinical outcome groups was determined as follows:

- SU = Subjects who passed both T1 and T2 challenges in PPOIT003
- DWSU = Subjects who were fully desensitised to cumulative 4950mg peanut protein at end • of treatment (passed T1 challenge) but failed the T2 challenge
- = Subjects who failed the T1 challenge irrespective of whether the reaction Allergic ٠ threshold in T1 challenge had increased from Baseline T0 challenge.

These clinical outcome groups are comprised of subjects in PPOIT-003 who received one of the treatment allocations outlined below however study staff and subjects remain blinded to their treatment allocation:

- PPOIT = Probiotic and peanut OIT taken daily for 18 months during PPOIT-003. •
- OIT = Probiotic placebo and peanut OIT taken daily for 18 months during PPOIT-003.
- = Probiotic placebo and OIT placebo taken daily for 18 months during PPOIT-003. Placebo .

All subjects will be monitored for 60 months (from 12 months post treatment -FO- to 72 months post treatment -F5).

The study consists of:

(FORM: SAP template interim analysis/Version 1.1)

Monitoring phase (up to 60 months)

This occurs after completion of the T3 visit of PPOIT-003, which coincides with the first visit of the follow-on study (F0). All subjects will be followed up for 60 months after T3/F0 (which is up to 6 years post treatment that was received in PPOIT-003). During this time, all subjects will be monitored for information on exposure to peanut/amount of peanut being eaten and allergic reactions via a mobile diary application (app) until the end of study (72 months post treatment (F5)).

A phone call will be administered at the following time points:

• Time point F1 – 12 months after F0 (24 months post-treatment)

A visit for SPT, bloods and stool will be administered at the following time points:

- Time point F2 24 months after F0 (36 months post-treatment)
- Time point F3 36 months after F0 (48 months post-treatment)
- Time point F4 48 months after F0 (60 months post-treatment)
- Time point F5 60 months after F0 (72 months post-treatment)

Note: Where a face-to-face visit is not possible (eg due to COVID-19 restrictions or other unavoidable circumstances), the visit will be conducted by phone and SPT, bloods and stool test will not be performed.

This study is expected to run for 78 months from the start of participant enrolment to the last participant finishing the study. The length of the study (i.e. follow up period) for each participant is 60 months.

The three sites will be: The Royal Children's Hospital Melbourne / Murdoch Children's Research Institute, The Women's and Children's Hospital Adelaide, Perth Children's Hospital. A maximum of 201 participants will be recruited – the study population recruited to PPOIT-003.

Study population

Subjects meeting the eligibility criteria will be recruited at end of PPOIT-003 without unblinding of PPOIT-003 treatment allocation.

Inclusion criteria

Subjects are eligible for the study if they meet all of the following criteria:

- Were randomised and received at least 1 dose of treatment in PPOIT-003
- Participated in the PPOIT-003 randomised trial
- Written informed consent from participants and/or parent/guardian.

Exclusion criteria

Subjects are not eligible for the study if they meet any of the following criteria:

- Are taking probiotic supplements (does not include formula, yoghurts and fermented foods).
- Withdrew from the PPOIT-003 study.
- Have any condition that, in the opinion of the Investigator, precludes participation for reasons of safety.

Sample size

No formal sample size calculation is being conducted for the follow-up study. A maximum of two hundred and one (201) participants will be recruited from PPOIT-003 trial (PPOIT n=79; OIT n=83; placebo n=39).

2.2. DESCRIPTION AND SCHEDULE OF INTERIM ANALYSIS

Interim analyses of the F1, F2, F3 and F4 data will be performed after all enrolled subjects have completed the F1, F2 and F3 study time points or withdrawn from the study at F1, F2 and F3 study timepoints, respectively. Analysis will be conducted using available data collected to the F1, F2 and F3 time point and will comprise primary and secondary outcomes (where relevant). This SAP is for the interim analysis of the F1 data. Summary tables will report data aggregated by treatment group and/or clinical outcome, with no individual subjects being identified.

Unblinding

Subjects' treatment allocation from PPOIT-003 will remain blinded throughout the duration of this follow-on study. Subjects will keep the same study number allocated from the parent study. Trial drug codes of the PPOIT-003 trial will be made available only to the unblinded study statistician and other unblinded independent consultants after database lock at the interim analysis and at the end of the study. All other study staff who are involved in the PPOIT-003 follow on study and assessments on the subjects, as well as the subjects themselves, will remain blinded to the allocation received during the PPOIT-003 study until the completion of the follow-on study.

3. POPULATIONS OF INTERIM ANALYSIS

The analysis of all outcome data will include all subjects who were randomised to PPOIT-003 trial and consented to roll over to PPOIT-003LT, where outcome data is available at the F1 time point.

4. VARIABLES

4.1. OUTCOMES

Table 1 –Outcomes description

	Outcome	Description
А	Peanut ingestion (intentional or accidental)	Binary outcome
	between T1 and F1	
		1=Yes if ingested peanut at least once over
		the 12 months period.
		0=No
В	Reaction to peanut ingestion (intentional or	Binary outcome
	accidental) between T1 and F1	1=Yes if reacted to peanut at least once
		over the 12 months period
		0=No
С	Number of reactions to peanut ingestion	Continuous outcome
	(intentional or accidental) T1 and F1 overall	
	and by severity	and Categorical outcome
		1=1 reaction
		2=2 reactions
		3=3 or more reactions
D	Use of EpiPen to treat reaction to peanut	Binary outcome
	(intentional or accidental) between T1 and F1	1=Yes if used EpiPen to treat reaction to
	(peanut at least once over the 12 months
		period
		0=No
E	Number of times using EpiPen to treat	Continuous outcome
-	reactions to peanut (intentional or accidental)	
	between T1 and F1	
F	Weekly average quantity of peanut protein	Continuous outcome
	ingested (intentional or accidental) between	
	F0 and F1	and Categorical outcome
		1=Never ingested
		2=Minimal amount (less than 1 peanut,
		<250g)
		3=Small amount (1-2 peanuts, 250-599g)
		4=Moderate amount (3-8 peanuts, 600-
		1999g)
		5=Large amount (>2000g)
G	Weekly average frequency of peanut	Continuous outcome
	ingestion (intentional or accidental) between	
	F0 and F1	and Categorical outcome
		1=Nil
		2=Less than once a month
		3=Once a month to <1/week
		4=1-2 times/week
		5=3-5 times/week
		6=>5 times a week
н	Quality of life scores – total, sub-scores	Continuous outcome. From FAQLQ-PF, tot
	(emotional impact, food anxiety, social and	score is calculated as the mean of up to 30
	dietary limitations) and FAIM total score at F1	items (some are age specific), with
		response scale from 0 (minimal impairmer
		in QoL) to 6 (maximal impairment in QoL).

		The mean scores for selected items are used to construct the sub-scores. The FAIM consists of 4 questions, scored on a 7-point scale. The FAIM total score is the mean of all items and ranges from 0 (limited severity perception) to 6 (greatest severity perception).
I	Change in quality of life scores (total, sub- scores, and FAIM) from screening in PPOIT- 003 study to F1	Continuous outcome

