4.2. OTHER VARIABLES

These variables are for purposes of describing the study sample.

Characteristics at the screening visit of PPOIT003: age, weight/height, medical history, skin prick test (peanut, egg, milk, cashew, almond, pistachio, hazelnut, dust mite and positive and negative control), blood and faecal sample (faecal sample collected by parents at home), anaphylaxis education.

Characteristics at the F0/T3 visit: age, weight/height, medical history, skin prick test (peanut, egg, milk, cashew, almond, pistachio, hazelnut, dust mite and positive and negative control), blood and faecal sample (faecal sample collected by parents at home), anaphylaxis education.

Characteristics at the F1 time point:

- An Allergy Questionnaire collected information on allergic disease (food allergies, asthma, eczema), medications, and peanut ingestion (accidental or intentional, amount, frequency).
- Parents of children aged 0-12 years will complete a validated Food Allergy Quality of Life-Parent Form (FAQLQ-PF) to report their child's health-related quality of life from the child's perspective. Children aged 8–12 years will complete the Food Allergy Quality of Life-Child Form (FAQLQ-CF) to specifically capture quality of life from the child's perspective. Children aged 13–17 years will complete the Food Allergy Quality of Life-Teenager Form (FAQLQ-TF) to specifically capture quality of life from the teenage child's perspective.

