5.2. F1 INTERIM ANALYSIS METHODOLOGY

Outcomes A, B, D

For these binary outcomes, they will be summarised as the number and proportion of children who had the outcome as yes between F0 and F1 by treatment groups and by clinical outcome groups.

The comparison between treatment groups will be made using a GLM approach with Gaussian error distribution (to avert convergence difficulties with low prevalence outcomes), linear link function and a cluster-robust standard error calculation to account for clustering by study site. The RD and 95% CI will be derived, adjusted by the age group at randomisation (1-5 years; 6-10 years) and SPT wheal size (≤10mm; >10mm).

The RR (with 95% CI) comparing treatments will also be estimated using a GLM approach (the "modified Poisson" approach of Zou, employing the Poisson family, a log link function and a cluster-robust standard error calculation to account for clustering by site), adjusted by the age group at randomisation (1-5 years; 6-10 years) and SPT wheal size (≤10mm; >10mm).

The comparison between clinical outcome groups will be made using a binary regression model. The RD, RR and 95% CIs will be derived.

Outcome C, F, G

For these categorical outcomes, they will be summarised as the number and proportion of children who had the outcome in each category by treatment groups and by clinical outcome groups. They will also be summarised as the median, IQR and range by treatment groups and by clinical outcome groups.

Outcomes C, E, F, G, I

For these continuous outcomes, they will be summarised as mean and SD or median and IQR by treatment groups and by clinical outcome groups as specified.

The mean difference between treatment groups will be obtained by using GLM to account for clustering by site, adjusted by the age group at randomisation (1-5 years; 6-10 years) and SPT wheal size (≤10mm; >10mm). The median difference using quantile regression model to adjust for the stratification factors if not normally distributed.

The mean difference between clinical outcome groups will be obtained by using a linear regression model. The median difference using quantile regression model if not normally distributed. For outcome I, linear/quantile regression model will be used for further adjusted for baseline QoL score.

Outcome H

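### Reactions and EpiPen use (outcomes B to E) are compared per child between the SU, DWSU and Allergic groups with no exposure-based measure, although these groups were told to eat peanut freely, eat it daily or avoid it

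*SAP*

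**What the plan says.** Section 2.1 of the SAP links peanut intake to the clinical outcome reached in the parent trial. SU children were to introduce "peanut into their diet ad libitum without specific instructions on how often or how much peanut to ingest". DWSU children were "instructed to ingest 1-2 peanuts each day to maintain desensitisation". Allergic children "were instructed to continue with strict peanut avoidance".

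Table 1 (section 4.1) then defines the reaction outcomes per child. Outcome B is "1=Yes if reacted to peanut at least once" in the period, and D is the same for EpiPen use. C is the number of reactions, and E is "Number of times using EpiPen to treat" reactions. None has a denominator other than the child.

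For A, B and D, section 5.2 says "they will be summarised as the number and proportion of children who had the outcome as yes between F0 and F1", by treatment group and by clinical outcome group, with risk differences and relative risks. C and E are compared by mean or median difference. The treatment-group models adjust for age group and SPT wheal size and allow for site. The clinical-group models name no covariate for B to E; the only one named anywhere is baseline quality of life, for outcome I.

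Exposure is collected. The F1 questionnaire (section 4.2) covers "peanut ingestion (accidental or intentional, amount, frequency", and outcomes A, F and G report it. They are analysed as separate outcomes and are never a denominator, offset, covariate or restriction for B to E.

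**The concern.** Objective 1 asks for reactions to peanut to be compared between SU, DWSU and Allergic children. Any reader of that comparison will want to know whether children who reached SU or DWSU react less readily than those who stayed allergic. The planned measure cannot show this alone, because the number of chances to react was set by group. An avoider who ate nothing is counted as reaction-free on the same footing as a child who ate peanut daily for a year without trouble.

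The consequence is a possible reversal: avoiders could appear safer than desensitised children purely because they had little or no exposure. Section 5.1 adds to the risk by calling the risk difference and relative risk between clinical outcome groups measures of treatment effect.

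**Working it through.** **No figure to reproduce.** The SAP states no reaction rate, ingestion count or outcome-group mix, and no sample size calculation. What follows shows only how the per-child measure behaves.

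**Inputs.** Daily eating gives k = 365 occasions a year, from the DWSU instruction if followed. Everything else is assumed: the risk per ingestion r in each group, and the avoiders' average number of accidental exposures k.

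**Formula.** Probability of at least one reaction in a year = 1 − (1 − r)^k.

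**Step 1: equal risk per ingestion.** A daily eater (k = 365) against a child with one accidental exposure (k = 1):

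| r in both | Daily eater | One exposure | Per-child RR | Per-ingestion ratio |
|---|---|---|---|---|
| 0.0005 | 16.7% | 0.05% | 334 | 1 |
| 0.001 | 30.6% | 0.1% | 306 | 1 |
| 0.005 | 84.0% | 0.5% | 168 | 1 |

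The two children are equally reactive, so exposure alone produces the whole contrast. Both have eaten peanut at least once, so restricting to ingesters would not remove it. That is why a rate per occasion is needed as well.

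**Step 2: avoiders much more reactive per ingestion.** Avoiders: r = 0.05, 0.2 or 0.5, with k = 0.2, 1 or 2 a year. Daily eaters: r = 0.0005, 0.001 or 0.002. Selected results, RR being daily eaters against avoiders:

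| Avoiders r, k | Daily r | Avoiders | Daily | Per-child RR | Per-ingestion ratio |
|---|---|---|---|---|---|
| 0.5, 2 | 0.0005 | 75% | 16.7% | 0.22 | 0.001 |
| 0.2, 1 | 0.0005 | 20% | 16.7% | 0.83 | 0.0025 |
| 0.2, 1 | 0.001 | 20% | 30.6% | 1.53 | 0.005 |
| 0.05, 0.2 | 0.002 | 1.0% | 51.8% | 50.8 | 0.04 |

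The first and last rows are the extremes of the 27 combinations. The per-child RR is above 1 in 19 of them and below 1 in 8. These counts describe the grid and are not probabilities. The per-ingestion ratio favours the daily eaters in every combination.

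**Step 3: time windows.** Table 1 labels A to E as T1 to F1, yet where it defines A, B and D it refers to 12 months. By section 2.1, F1 is 24 months after treatment and F0 is 12 months after, so T1 to F1 spans 24 months and F0 to F1 spans 12. F and G cover F0 to F1, and section 5.2 summarises A, B and D over F0 to F1. Events and exposure cannot be combined until one window is fixed.

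**The case against.** **Objective 1 asks for intake and reactions side by side, and per-child occurrence answers that.** This stands as a reason to keep the per-child analysis. It does not make that analysis informative about reactivity between groups whose intake was set by instruction.

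**Exposure is already tabulated, and much can be read off.** A reaction to eating peanut requires eating it, so the proportion reacting among ingesters is the B count divided by the A count, if windows agree and no items are missing. That is fair, and no one could say the objective becomes uninterpretable. But the plan provides no contrast or interval among ingesters, and separate tables of A, F and G cannot yield a rate per ingestion.

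**A reader might infer that the randomised comparison is faulty too.** The documents do not support this. Instructions followed clinical outcome, not arm, so intake is a consequence of treatment, and the as-randomised per-child contrast is a legitimate total effect. Suppose group risks of 9.9% (SU), 30.6% (DWSU) and 13.9% (Allergic), with assumed mixes of 50/20/30 in an active arm and 5/5/90 in placebo. The arm risks are then 0.5×0.099 + 0.2×0.306 + 0.3×0.139 = 15.2% and 0.05×0.099 + 0.05×0.306 + 0.9×0.139 = 14.5%. That near-null would be a true one for the total effect. Restricting to ingesters or offsetting by intake would condition on a post-randomisation variable.

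**A reader might also infer that the contrast mostly measures who ate peanut.** No rate in the SAP supports that. In the same assumed figures SU still looks safer than Allergic per child, and only DWSU against Allergic reverses.

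**An exposure-based rate has its own faults.** A log offset is undefined for children with no ingestion. Avoiders' symptom-free accidental exposures may pass unnoticed, which would inflate their rate. Both points stand and shape the fix.

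**Conclusion.** The point holds for SU against DWSU against Allergic. The plan compares B to E per child, intake was set by instruction in exactly these groups, and no exposure-based measure is planned, so the contrast mixes intake with reactivity and can reverse. Under the assumed rates, the per-child RR for daily eaters against avoiders lies anywhere from 0.22 to 51 while the per-ingestion ratio is 0.001 to 0.04. With equal reactivity it is 168 to 334. Size and direction in the actual data are unknown; only the 365 occasions a year comes from the SAP, and it assumes that the instruction was followed.

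The point does not extend to PPOIT, OIT and placebo, where the per-child comparison is valid as a total effect and needs only that label. It should be changed before the F1 results are interpreted, because it decides what Objective 1 can conclude about the clinical outcome groups.

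**What to change.** 1. Keep the per-child analyses of B to E as the burden measure. Label the comparison between randomised arms as a total effect that includes any effect through intake.
2. Fix one window for events and exposure, and reconcile Table 1 with section 5.2.
3. For the clinical outcome groups, add the proportion with a reaction, and with EpiPen use, among children with A = Yes, with risk difference, relative risk and 95% CI.
4. For the same groups, add reactions and EpiPen uses per ingestion occasion among children with non-zero ingestion, from a Poisson or negative binomial model with the log ingestion count as offset. The count can be taken from the continuous form of G multiplied by the weeks in the window. Report how many children are excluded for zero ingestion.
5. Base statements about reactivity between clinical outcome groups on items 3 and 4 together, not on per-child risk alone.
6. If items 3 or 4 are also shown by randomised arm, mark them descriptive, because ingestion is post-randomisation.

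The cost is SAP wording and a few extra tables, with no new data. The rates will be imprecise in avoiders and may be too high there if exposures without symptoms go unnoticed; the report should say so.

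### Outcome F's peanut protein bands are printed in grams where milligrams are meant, leave gaps between categories, and do not say whether they apply to a weekly total or to each ingestion

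*SAP*

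**What the plan says.** SAP section 4.1, Table 1, defines outcome F as "Weekly average quantity of peanut protein" ingested between F0 and F1, to be handled both as a continuous and as a five-level categorical variable. Level 1 is no ingestion. The other levels are:

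- "2=Minimal amount (less than 1 peanut", paired with a bound of less than 250 g;
- "3=Small amount (1-2 peanuts, 250-599g";
- "4=Moderate amount (3-8 peanuts, 600", running to 1999 g;
- "5=Large amount (>2000g", with no peanut count.

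Section 2.1 states peanut protein in milligrams: the group desensitised without sustained unresponsiveness (DWSU) is described as "fully desensitised to cumulative 4950mg peanut protein at end" of treatment. The same section says that this group was "instructed to ingest 1-2 peanuts each day to maintain desensitisation". The SAP gives no protein content per peanut, and does not say whether the counts in Table 1 are per occasion, per day or per week.

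**The concern.** The bands are operative coding rules for an outcome that serves the first objective (peanut intake after treatment). Section 5.2 reports outcome F as the number and proportion of children in each category, by treatment group and by clinical outcome group.

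Three things are unsettled. The unit is inconsistent with the peanut counts beside it and with section 2.1. The bands do not cover every possible value. The counts read like an amount per occasion or per day, while the variable is a weekly average. A programmer following the table literally would produce an uninformative summary. Two programmers who each corrected it silently could still code the same child differently.

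**Working it through.** **Inputs.** Band limits 250, 599, 600, 1999 and 2000, and peanut counts 1-2 and 3-8 (section 4.1, Table 1); cumulative challenge of 4950 mg and intake of 1-2 peanuts a day (section 2.1).

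**1. Protein per peanut implied by the table** (band limit divided by paired count).

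- Category 3: 250/1 = 250 and 599/2 = 299.5.
- Category 4: 600/3 = 200 and 1999/8 = 249.9.

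As printed, one peanut would hold about 200-300 g of protein. Read in mg, it holds 200-300 mg, and the 4950 mg challenge equals 4950/250 = 19.8 peanuts at 250 mg each. The milligram reading is coherent; the gram reading is not.

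**2. Literal coding in grams.**

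- 250 g / 4.95 g = 50.5 full challenges a week to leave category 2.
- In peanuts: 250,000 mg / 300 mg = 833, up to 250,000 / 200 = 1250 a week.
- To reach category 5: 2,000,000 / 300 = 6667, up to 2,000,000 / 200 = 10,000 a week.
- The whole challenge dose, 4.95 g, is itself category 2.

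**3. Coverage of the bands.** Applying the printed limits, the values 599.5, 1999.5 and 2000 return no category. This is so in either unit.

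**4. Labels against protein limits, read in mg.** For 8 peanuts:

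| mg per peanut | 8 peanuts | Category from protein |
|---|---|---|
| 200 | 1600 mg | 4 |
| 250 | 2000 mg | none |
| 300 | 2400 mg | 5 |

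The label puts 8 peanuts in category 4. That needs at most 1999/8 = 249.9 mg per peanut, while placing 1 peanut in category 3 needs at least 250 mg. No single conversion meets both exactly. The mismatch is small, but it shows that the labels and limits have not been checked against one stated figure.

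**5. Time basis.** One to two peanuts a day is 7-14 a week:

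| mg per peanut | 7 a week | 14 a week | Categories |
|---|---|---|---|
| 200 | 1400 mg | 2800 mg | 4, 5 |
| 250 | 1750 mg | 3500 mg | 4, 5 |
| 300 | 2100 mg | 4200 mg | 5, 5 |

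Read per occasion or per day, the label gives category 3. In the other direction, 8 peanuts once a month averages 8 × 200 × 12/52 = 369 mg to 8 × 300 × 12/52 = 554 mg a week, which is category 3, although the label for 8 peanuts is category 4.

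**The case against.** The intended unit is evident from the peanut counts in the same cells, so a careful programmer would probably read mg. The factor of 1000 then measures the slip and not an effect on results. This stands as a limit on the harm, but the gaps and the time basis survive that silent correction.

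The categorical version is used descriptively only. Section 5.2 compares groups on outcome F through mean or median differences of the continuous version, and intake is also covered by outcome A (any ingestion) and outcome G (frequency). This stands in full. A reader might infer that the groups could not be told apart on intake; the SAP does not support that.

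A reader might also infer that 8 peanuts cannot be coded, or belongs in the top band. Neither follows. The table assigns a count of 8 to category 4, and the collision with 2000 arises only at 250 mg per peanut, a figure that the SAP does not state.

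Finally, the bands can be applied to a weekly total, and a child eating 7-14 peanuts a week would then properly be Moderate or Large. Nothing in the SAP says that category 3 is meant to match the intake instruction for the DWSU group. The mismatch is therefore an ambiguity to be settled and not a proven error, and it gives no ground for multiplying the bands by 7.

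**Conclusion.** The concern holds in three parts.

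- The unit is wrong by a factor of 1000. This follows from the SAP alone. Literal coding would put every realistic eater in category 2 and make the categorical summary uninformative.
- The bands are not contiguous at 599-600 and 1999-2000, with 2000 itself uncovered. This is certain and independent of the unit.
- The time basis is not stated. The choice can move a child eating 1-2 peanuts a day from category 3 to category 4 or 5. This rests on 200-300 mg per peanut, inferred from the table's own limits, and on that intake being kept up through the week.

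The effect is confined to the descriptive category table. The planned comparisons of outcome F do not use the bands. The point concerns outcome coding and judges no intake instruction. It should be corrected before programming.

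**What to change.** In Table 1, outcome F:

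1. Replace g by mg in all four bands, and state the same unit for the continuous version.
2. Make the bands contiguous: <250; 250 to <600; 600 to <2000; ≥2000 mg.
3. State the peanut-to-protein conversion used, then check each peanut-count label against it and reword any that does not fit.
4. State whether the bands apply to the weekly average total or to the amount per ingestion, and word the labels accordingly.

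The cost is a table edit and the matching line in the analysis program. No new data are needed, and the continuous analysis is unchanged.
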